4.3.2 Prohibited Therapy

The following treatments are prohibited during study treatment:

Investigational or unlicensed/unapproved agents of any type

Patients receiving any of the prohibited therapies will be discontinued and assessed for safety at end-of study visit

4.4 STUDY ASSESSMENTS

4.4.1 Description of Study Assessments

For the timing of each assessment listed in this section, refer to Section 4.4.2 and Appendix 1.

4.4.1.1 Medical History and Demographic Data

Medical history includes clinically significant diseases and all medications (e.g., prescription drugs, over-the-counter drugs, herbal or homeopathic remedies, nutritional supplements)

Recormon—F. Hoffmann-La Roche Ltd

Protocol ML29005, Version 3.0 dated 12 Sep 2016

28

used by the patient within 4 weeks prior to the screening visit. RBC transfusion needed within 8 weeks prior to the screening will be recorded.

Demographic data will include weight, height, age and gender.

4.4.1.2 Physical Examinations

A complete physical examination should include an evaluation of the head, eyes, ears, nose, and throat, and the cardiovascular, dermatological, musculoskeletal, respiratory, gastrointestinal, genitourinary, and neurological systems. Any abnormalities identified at screening should be recorded on the General Medical History and Baseline Conditions eCRF.

At subsequent visits (or as clinically indicated), limited, symptom-directed physical examinations should be performed. Changes from baseline abnormalities should be recorded in patient notes. New or worsened clinically significant abnormalities should be recorded as adverse events on the Adverse Event eCRF.

4.4.1.3 Vital Signs

Vital signs will include measurements of respiratory rate, pulse rate, and systolic and diastolic blood pressure while the patient is in a seated position, and body temperature.

4.4.1.4 Laboratory Assessments

Samples for the following standard laboratory tests will be sent to the study site's local laboratory for analysis. The results from these assessments should be available on visit date, prior to the Recormon® administration:

- Haematology parameters will include haemoglobin (Hb), red blood cell count (RBC), white blood cell count (WBC) and differentials, and platelet count.
- Biochemistry parameters at screening will include serum EPO, serum creatinine, alanine aminotransferase (ALT/SGPT) and aspartate aminotransferase (AST/SGOT). Biochemistry parameters at any further time point during the study will include ALT/SGPT, AST/SGOT, and serum creatinine. Serum ferritin will include at screening and end-of-study visit.

4.4.2 Timing of Study Assessments

4.4.2.1 Screening Assessments

Written informed consent for participation in the study must be obtained before performing any study-specific screening tests or evaluations. Informed Consent Forms for enrolled patients and for patients who are not subsequently enrolled will be maintained at the study site.

Screening tests and evaluations will be performed within 14 days prior to the start of study drug administration, unless otherwise specified.

Results of standard-of-care tests or examinations performed prior to obtaining informed consent and within 14 days prior to the start of study drug administration may be used; such tests do not need to be repeated for screening. These will include the following:

Recormon—F. Hoffmann-La Roche Ltd

Protocol ML29005, Version 3.0 dated 12 Sep 2016

29

- Review and documentation of demographics data and medical history
- Review and documentation of MDS diagnosis
- IPSS score
- Physical examination
- Vital sign measurements
- Haematology and biochemistry laboratory tests
- AE recording (Note: after informed consent has been obtained but prior to initiation of study drug, only SAEs caused by a protocol-mandated intervention should be reported).
- Recording concomitant treatments and therapies
- Recording RBC transfusion needed within the past 8 weeks
- Serum pregnancy test for female patients of childbearing potential. Patients who are amenorrheic for at least 12 months are not considered of childbearing potential.

All screening evaluations must be completed and reviewed to confirm that patients meet all eligibility criteria before enrolment. The investigator will maintain a screening log to record details of all patients screened and to confirm eligibility or record reasons for screening failure, as applicable.

Patients who fail screening may be re-screened if it is considered likely that they could later become eligible. There is a limit of 2 screening attempts for each patient. Re-consenting process must be performed.

Please see Appendix 1 for the schedule of screening assessments.

4.4.2.2 Assessments during Treatment

All assessments must be performed on the day of the specified visit (V1 – V4), unless a time window is specified in the schedule of assessments (see Appendix 1). Assessments scheduled on the visit date should be performed prior to administration of study treatment, unless otherwise noted in the schedule of assessments.

At each treatment visit, patients will undergo the following assessments:

- Physical examination and measurements of vital signs
- Routine laboratory tests (see section 4.4.1.4 for details about individual laboratory assays). The results from these tests should be available on visit date prior to the Recormon® administration.
- AE recording
- Recording concomitant treatments and therapies
- Recording RBC transfusion needed from previous visit
- Recormon® dose adjustment will be performed at week 4±1 (see section 4.2.2.1 for details about dose adjustment)

Please see Appendix 1 for the schedule of assessments performed during the treatment period.

4.4.2.3 Assessments at End of Study/Early withdrawal visit

End of study/early withdrawal visit will occur at 4 weeks after last dose of Recormon®. This visit will include the following evaluations:

- Physical examination and vital sign measurements
- Safety laboratory assessments (see section 4.4.1.4 for details about individual laboratory assays)
- AE recording
- Recording of concomitant treatments and therapies
- Recording of RBC transfusion needed from previous visit

Please see Appendix 1 for the schedule of assessments performed at the end-of-study visit/early termination visit.

4.4.2.4 Assessments at Unplanned Visits

Assessments other than those specified in Appendix 1, Schedule of Assessments, may be performed as clinically indicated. These assessments should be adequately documented.

4.5 PATIENT, STUDY AND SITE DISCONTINUATION

4.5.1 Patient Discontinuation

The investigator has the right to discontinue a patient from study drug or withdraw a patient from the study at any time. In addition, patients have the right to voluntarily discontinue study drug or withdraw from the study at any time for any reason. In case of such withdrawal, the reason(s) for withdrawal must be documented. Reasons for discontinuation of study drug or withdrawal from the study may include, but are not limited to, the following:

- Patient withdrawal of consent at any time
- Any medical condition that the investigator or Sponsor determines may jeopardize the patient's safety if he or she continues in the study

4.5.1.1 Discontinuation from Study Drug

Reasons for study drug discontinuation may include, but are not limited to the following:

- Evolution into high-risk MDS or overt leukemia as determined by Investigator
- Withdrawal of consent by the patient
- Any significant AE that compromises the patient's ability to participate in the study
- Investigator or Sponsor determines it is in the best interest of the patient
- Intercurrent illness
- Treatment unresponsiveness
- Need for prohibited treatment
- Protocol violation
- Pregnancy

Patients who discontinue study drug prematurely will be asked to return to the clinic for the end-of-study visit (see Section 4.4.2.3). The primary reason for premature study drug

Recormon—F. Hoffmann-La Roche Ltd

Protocol ML29005, Version 3.0 dated 12 Sep 2016

31

discontinuation should be documented on the appropriate eCRF. Patients who discontinue study drug prematurely will not be replaced.

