3. STUDY DESIGN

3.1 DESCRIPTION OF STUDY

3.1.1 Overview of Study Design

This is a phase IV, prospective, multi-centre, open label study to assess the efficacy of Recormon® for treating anemic patients with low/intermediate-1 risk MDS, in approximately 120 adult patients. The primary efficacy endpoint is a proportion of patients achieving erythroid response at week 12 according to IWG 2006 definition. The trial will be conducted at approximately 8 centres nationwide.

All potential study patients must provide signed written informed consent approved by the relevant independent Ethics Committee before undergoing any study-specific procedures. Results of the screening assessments must be available and patients must meet all eligibility criteria prior to enrolment into the study. The study design is shown in Figure 1.

[figure not shown]

Figure 1 Study Scheme

The study consists of a 2-week screening period, a 12-week treatment phase and end-of-study visit (see figure 1). After screening, eligible patients will be treated with epoetin beta (Recormon®) as recommended in the approved label and international guidelines for the use of epoetin in MDS patients, Recormon® dosage will be adjusted on the basis of erythroid response.

During screening period, serum level of endogenous erythropoietin will be assessed, as well as liver and kidney function. Bone marrow morphology analysis and karyotyping are also performed during screening if they have not been assessed in the 6 months prior to participation in the study. Complete blood count test is performed during screening period and at every patient's visit until the end of study visit. The result should be available prior to dosing of Recormon®.

The patient's erythroid response will be assessed at week 4 and every 4 weeks thereafter, until end-of-study visit. Patients who achieve Hb level ≥ 12 g/dL will stop treatment, while

Recormon—F. Hoffmann-La Roche Ltd

Protocol ML29005, Version 3.0 dated 12 Sep 2016

23

patients with Hb level < 12 g/dL will continue treatment for the total of 12 weeks. Concurrent G-CSF can be administered upon physician discretion.

Patients can withdraw from the study at any time as per section 4.5.1

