3.4 OUTCOME MEASURES

3.4.1 Efficacy Outcome Measures

The efficacy outcome measures for this study are as follows:

Primary Efficacy Outcomes:

- The cumulative proportion of patients achieving erythroid response at week 12 according to IWG 2006 definition as
 - Hb increase by ≥ 1.5 g/dL
 - Reduction of units of RBC transfusions by an absolute number of at least 4 RBC transfusions/8 weeks compared with the pre-treatment transfusion number in the previous 8 weeks. Only RBC transfusions given for a Hb of ≤ 9.0 g/dL pre-treatment will count in the RBC transfusion response evaluation

Secondary Efficacy Outcomes:

- % patients with platelet response (pre-treatment $< 100 \times 10^9/L$) at week 12 defined by IWG 2006 as following:
 - Absolute increase of $\geq 30 \times 10^9/L$ for patients starting with $> 20 \times 10^9/L$ platelets (Increase from $< 20 \times 10^9/L$ to $> 20 \times 10^9/L$ and by at least 100%)
- % patients with neutrophil response (pre-treatment $< 1.0 \times 10^9/L$) at week 12 defined by IWG 2006 as following;
 - At least 100% increase and an absolute increase $> 0.5 \times 10^9/L$

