6.2 ANALYSIS POPULATION

The efficacy analysis will be performed based on the intent-to-treat (ITT) population defined as all enrolled patients who receive at least one dose of study medication.

The Safety population will include all patients who receive at least one dose of study medication.

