- The Thai Society of Hematology. Guideline for diagnosis and management of Myelodysplastic Syndrome (www.tsh.or.th/files_news/newsFile_20110512140230.doc)

Appendix 1

Schedule of Assessments

	Screening	treatment phase				End-of-Study visit
Visit	S1	V1	V2	V3	V4	F
Week	-2	0	4	8	12	15 ^a
Visit window ± (week)			1	1	1	1
Informed consent ^b	X					
Medical history	X					
Physical examination/vital signs	X	X	X	X	X	X
CBC ^c	X	X	X	X	X	X
Liver function test ^d	X	X	X	X	X	X
Creatinine	X	X	X	X	X	X
Serum EPO	X					
Serum Ferritin	X					X
Serum pregnancy ^e	X					
Record of RBC Transfusion	X	X	X	X	X	X
Concomitant treatment	X	X	X	X	X	X
Adverse event		X	X	X	X	X
Drug dispensing ^f		X	X	X		

^a In case of early discontinuation, end-of-study for safety follow up must be undertaken 4 weeks after the last study drug administration (unless the reason for early withdrawal is withdrawal of consent)

^b Written informed consent is required before performing any study-specific tests or procedures. Signing of the Informed Consent Form can occur outside the 14-day screening period.

^c Parameters will include haemoglobin (Hb), red blood cell count (RBC), white blood cell count (WBC) and differentials, and platelet count

^d Liver function test includes alanine aminotransferase (ALT/SGPT), aspartate aminotransferase (AST/SGOT)

All women of childbearing potential (including those who have had a tubal ligation) will have a serum pregnancy test at screening. Patients who are amenorrhoeic for at least 12 months are not considered of childbearing potential.

^f If haemoglobin level reaches ≥ 12 g/dL at any time, Recormon[®] should be discontinued until Hb levels are ≤ 10 g/dL.

Appendix 2

International Prognostic Scoring System (IPSS)

(Greenberg et.al, 1997)

The 1997 International Prognostic Scoring System (IPSS) for De Novo Myelodysplastic Syndrome

Prognostic Factor	Category Score ^a				
	0 (best)	0.5	1	1.5	2 (worst)

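### No week-12 haemoglobin or transfusion assessment is required from patients who stop study drug early without withdrawing consent, although the ITT primary endpoint is response at week 12

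*Protocol*

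**What the plan says.** Analysis set and endpoint. Protocol section 6.2 bases efficacy on an ITT population, "defined as all enrolled patients who receive at least one dose of study medication". Section 3.4.1 gives the primary outcome as "The cumulative proportion of patients achieving erythroid response at week 12 according to IWG 2006 definition as" a haemoglobin rise of at least 1.5 g/dL or a reduction in transfusions. Section 6.4.1 reports the percentage achieving this at week 12.

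Early stopping. Section 4.5.1.1 states: "Patients who discontinue study drug prematurely will be asked to return to the clinic for the end-of-study visit". Section 4.4.2.3 fixes the timing: "End of study/early withdrawal visit will occur at 4 weeks after last dose of Recormon". Footnote a to the schedule in Appendix 1 gives the purpose: "In case of early discontinuation, end-of-study for safety follow up must be undertaken 4 weeks after the last study drug administration". Section 4.5.1.1 lists lack of response to treatment among the reasons for stopping and says that stoppers are not replaced. Section 4.5.1.2 deals separately with withdrawal from the study and rules out follow-up once consent has been withdrawn.

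Data that are collected. Section 3.1.1 says: "Complete blood count test is performed during screening period and at every patient's visit until the end of study visit". It adds: "The patient's erythroid response will be assessed at week 4 and every 4 weeks thereafter, until end-of-study visit". The exit visit also includes "Recording of RBC transfusion needed from previous visit" (section 4.4.2.3).

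**The concern.** The analysis set and the follow-up rule do not fit together. The ITT set takes in every dosed patient and asks for status at week 12. The follow-up rule ties the last required visit to the last dose, not to week 12. Sections 4.5.1.1 and 4.5.1.2 distinguish stopping drug from leaving the study, yet a patient who has only stopped drug is given nothing beyond the exit visit.

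Two things are at stake. First, a statistical analysis plan can assign a status to a patient without a week-12 value, but it cannot supply a haemoglobin result or transfusion count that was never scheduled. Second, some patients will stop because they are not responding, so the absence of data may be linked to the outcome. In a single-arm study no comparison group would share the same loss.

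**Working it through.** **Step 1: the plan's own figures.** Inputs from section 6.1: 120 enrolled, 10% withdrawal, 108 evaluable, observed response rate 0.25.

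- Evaluable: 120 × 0.90 = 108.
- Half-width: 1.96 × √(0.25 × 0.75 / 108) = 0.0817, giving 0.1683 to 0.3317. This matches the stated figures.

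**Step 2: when the exit visit falls.** Exit week = week of last dose + 4. As a check on the convention, twelve weekly doses starting at week 0 end at week 11, and 11 + 4 = 15, the week Appendix 1 gives for the end-of-study visit. Appendix 1 allows ±1 week both for the week-12 visit (weeks 11 to 13) and for the exit visit.

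| Week of last dose | Exit visit (nominal) | Relation to weeks 11-13 |
|---|---|---|
| 0 to 5 | 4 to 9 | Before the window, even if one week late (latest 9 + 1 = 10) |
| 6 | 10 | Inside only if one week late (11) |
| 7 to 9 | 11 to 13 | Inside |
| 10 | 14 | Inside only if one week early (13); the text does not say whether the week-12 visit is still held |

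The gap therefore concerns patients whose last dose is at about week 6 or earlier.

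**Step 3: can earlier data stand in for week 12?** Only in part. Blood counts and transfusion records exist up to and including the exit visit. However, section 3.3.1 says that haemoglobin improvement is usually noted 6-8 weeks after an adequate dose is started, and Appendix 3 lists haematological improvement under a period of at least 8 weeks. A last dose at weeks 0-3 gives an exit at weeks 4-7, which is less than 8 weeks of observation.

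**Step 4: illustrative size.** The documents give no rate of early drug stopping, so the 10% withdrawal rate is borrowed as an assumption. Responders among the observed: 0.25 × 108 = 27. With 12 patients unknown:

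- all 12 non-responders: 27/120 = 22.5% (95% CI 15.0% to 30.0%);
- the 12 respond like the rest: 30/120 = 25.0% (17.3% to 32.7%);
- all 12 responders: 39/120 = 32.5% (24.1% to 40.9%).

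Against 25.0% among the observed, the shift runs from −2.5 to +7.5 points. Keeping 25% among the observed and varying the number unknown, 6 unknown gives 23.75% to 28.75%, and 24 unknown gives 20.0% to 40.0%. These are bounds, not expected bias.

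**The case against.** A reader might infer that early stoppers have no outcome at all, that the ITT analysis is in effect an analysis of completers, and that the response rate is inflated. The documents do not support this.

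- Blood counts and transfusions are recorded at every visit attended, including the exit visit. Last doses at weeks 7-9 put that visit inside the week-12 window.
- The primary outcome is called cumulative and response is assessed every 4 weeks, so a response seen before stopping might count. Combining cumulative with a fixed week leaves open which reading applies.
- No passage removes anyone from the analysis. A rule counting patients without a week-12 value as non-responders would give every dosed patient a status and would be conservative here. Such a rule is ordinary SAP content, and the SAP is not shown.
- A patient judged unresponsive after eight weekly doses has a last dose at about week 7 and exits at about week 11, inside the window. The link between missing data and non-response is therefore possible but not demonstrated.
- The direction is open. Section 3.1.1 has patients who reach Hb 12 g/dL stop treatment, so some who stop may be responders.
- The 10% is a withdrawal rate and may include consent withdrawals, who cannot be followed under any rule.
- The 10-point span between the bounds should not be set against the 8.17-point half-width. The full interval is 16.3 points wide, and neither shift (−2.5 or +7.5) exceeds the half-width.

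All of this stands, and it limits the point to a gap in required data collection. It does not close the gap: for last doses at weeks 0-5 no required visit lies in the week-12 window, and no analysis rule can create the missing measurement.

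**Conclusion.** The point holds in limited form. The protocol sets a week-12 endpoint for all dosed patients but does not require week-12 data from those who stop drug early without withdrawing consent. Last doses at weeks 0-5 clearly miss the window, and week 6 is borderline. Since lack of response is one listed reason for stopping, the response rate is at risk of bias. Neither the presence of bias nor its direction is shown.

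The 22.5% to 32.5% range rests on 12 of 120 patients being unknown and 25% of the rest responding. The true number of affected patients cannot be read from the protocol.

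One related ambiguity affects who is counted. Section 3.1.1 says treatment stops at Hb 12 g/dL or above, whereas section 4.2.2.1 and Appendix 1 footnote f describe discontinuation until Hb has fallen to 10 g/dL or below. If a site treats such a stop as premature discontinuation, a responder could be sent to the exit visit early. These passages must be reconciled. The point is a worthwhile, low-cost improvement and does not invalidate the design.

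**What to change.** Amend sections 4.5.1.1 and 4.4.2.3, with a matching footnote in Appendix 1. Patients who stop study drug but have not withdrawn consent should keep the remaining scheduled blood counts and transfusion records (V2 to V4) through week 12, in addition to the safety visit 4 weeks after the last dose. Reconcile sections 3.1.1 and 4.2.2.1 so that it is clear whether patients who stop at the haemoglobin threshold count as premature discontinuations. Leave the rule for patients still without a week-12 value to the SAP.

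The cost is a wording change plus one or two routine local-laboratory visits in a small number of patients. The change works only prospectively, because visits not held cannot be recovered at analysis, and it does nothing for patients who withdraw consent.

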4.5.1.2 Withdrawal from Study

Every effort should be made to obtain information on patients who withdraw from the study. The primary reason for withdrawal from the study should be documented on the appropriate eCRF. Patients will not be followed for any reason after consent has been withdrawn. Patients who withdraw from the study will not be replaced.

4.5.2 Study and Site Discontinuation

The Sponsor has the right to terminate this study at any time. Reasons for terminating the study may include, but are not limited to, the following:

- The incidence or severity of adverse events in this or other studies indicates a potential health hazard to patients.
- Patient enrollment is unsatisfactory.
- Steering committee decision
- The Sponsor will notify the investigator if the study is placed on hold, or if the Sponsor decides to discontinue the study.
- The Sponsor has the right to replace a site at any time. Reasons for replacing a site may include, but are not limited to, the following:
 - Excessively slow recruitment
 - Poor protocol adherence
 - Inaccurate or incomplete data recording
 - Non-compliance with the International Conference on Harmonization (ICH) guideline for Good Clinical Practice

5. ASSESSMENT OF SAFETY

5.1 SAFETY PLAN

Patients will be assessed by prior medical history, vital signs (including resting blood pressure, heart rate, and body temperature), weight and height, physical examination, AEs and concomitant medications. A complete medical history (including prior treatments for MDS) will be documented at screening. A general physical exam will be performed at screening, and at every treatment visit and end-of-study visit (see Appendix 1, Schedule of Assessments).

AEs will be monitored and documented continuously during the study. SAEs will also be documented and reported according to the ICH E2 Guideline for Clinical Safety Data Management, Definitions and Standards for Expedited Reporting. All AEs and SAEs (including patients' symptoms and signs of toxicity and clinically significant haematological and biochemical parameters) will be graded according to NCI CTCAE version 4.0.

Changes in concomitant medication will be recorded at each study visit.

